5.2 Exclusion criteria

Subjects meeting any of the following criteria are not eligible for inclusion in this study:

1. Head circumference $< - 2$ SD z-score in cm following WHO age and sex-specific reference curves (suspicion of microcephaly) (See [Section 16.1 Appendix 1](#))
2. Severe malnutrition (body mass index (BMI) less than 70% of median normalized WHO reference weight)
3. Presence of severe malaria (according to WHO 2015 definition - See [Section 16.4 Appendix 4](#))
4. Hemoglobin < 7 g/dL
5. HIV status:
 - in Cohort 1 : patient's or patient's mother's current treatment with ARV
 - in Cohort 2 : Mother's known HIV positive status at patient's birth or mother's current treatment with ARV
6. Presence of the following signs of a critical condition: apnea-bradycardia, sustained bradycardia, tachycardia, desaturation, hypotension, hypothermia; or other severely

deteriorated general condition (based on IMCI criteria in sick infants, WHO 2005 - See [Section 16.5 Appendix 5](#))

7. Presence of any clinically significant neurological condition:
 - any episode of convulsion during the present illness (in keeping with the IMCI list of general danger signs)
 - known neurological disorders (e.g. chronic seizure disorders, cerebral palsy)
8. Presence of clinically significant abnormality of the hepatic and renal systems
9. History of malabsorption or previous gastrointestinal surgery, or history of radiation therapy that could affect drug absorption or metabolism, or any other disorder or history of a condition that could interfere with drug absorption, distribution, metabolism, or excretion
10. Patients unable to swallow or whose drinking is impaired
11. Known hypersensitivity of the patient or either patient's parent to artemether, lumefantrine, any of the excipients of Coartem®/Riamet® Dispersible tablet, or to drugs of similar chemical classes
12. Known family history of congenital prolongation of the QT_c interval or sudden death or with any other clinical condition known to be associated with prolongation of the QT_c interval such as history of symptomatic cardiac arrhythmias, with clinically relevant bradycardia or with severe cardiac disease
13. Disturbances of electrolyte balance (e.g. hypokalemia or hypomagnesemia) - See [Section 16.1 Appendix 1](#) as an example for reference
14. Presence of any age-adjusted clinically or hematologically relevant laboratory and blood chemistry abnormalities

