15. Patients who received any antimalarial drug, including antibiotics with antimalarial activity, within 14 days of trial start, or any other prohibited drug (see [Table 6-2](#))
16. Patients who received an investigational drug within 5 half-lives of enrollment or participated in an investigational study or within 30 days, whichever is longer.

NOTE: Where information is either not available or insufficient (e.g. from medical history, charts) to assess whether a patient meets a specific exclusion criterion, the study site team shall use its best medical judgement to make an inclusion/exclusion decision for the patient.

6 Treatment

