6.2 Other treatment(s)

6.2.1 Concomitant therapy

Concomitant medication is defined as any medication, other than the study drug, which is given at least once between the day of first dose of study medication and the last visit of core follow-up period (including those which were started pre-baseline and continued into the treatment period), including prescription and over-the-counter medicines, and any traditional or herbal remedies.

The investigator should instruct the patient's legal guardian to notify the study site about any new medications the patient takes after the start of the study drug. All medications and significant non-drug therapies (including physical therapy and blood transfusions) administered after the patient starts treatment with study drug must be recorded on the appropriate CRF.

Similarly, all medications and significant non-drug therapies administered during the core follow-up period to a mother breastfeeding a patient after the patient starts treatment with study drug must be listed on the appropriate CRF.

Each concomitant drug must be individually assessed against all exclusion criteria/prohibited medication. If in doubt, the investigator should contact the Novartis medical monitor before entering a subject in the study or allowing a new medication to be started during the study. If the subject is already recruited, the investigator should also contact Novartis to determine if the subject should continue participation in the study.

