12.1 Analysis sets

The Full Analysis Set (FAS) comprises all subjects that received any study drug. Subjects will be analyzed according to the treatment(s) received.

The Safety Set includes all subjects who received at least one dose of study treatment. Subjects will be analyzed according to the study treatment received. The Safety set will be used for safety analyses while FAS will be used for other analyses.

The Per-Protocol Set (PPS) is a subset of subjects of the Full Analysis Set and is characterized by the following criteria:

- did not have important protocol deviations affecting efficacy
- took at least 80% of study medication
- PCR corrected cure status at Day 29 can be defined.

Important protocol deviations for exclusion from the PPS will be identified by the clinical team before database lock.

The PK set is a subset of the Full Analysis Set who had evaluable PK parameter data.

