2.2 Analysis sets

The Full Analysis Set (FAS) comprises all subjects that received any study drug and had *Plasmodium falciparum* present at Screening visit. Subjects will be analyzed according to the treatment(s) received as per protocol.

The Safety Set includes all subjects who received at least one dose of study treatment. Subjects will be analyzed according to the study treatment received as per protocol. The Safety Set will be used for safety analyses while FAS will be used for other analyses.

The Per-Protocol Set (PPS) is a subset of subjects of the Full Analysis Set and is characterized by the following criteria:

- did not have important protocol deviations affecting efficacy
- took at least 80% of study medication
- PCR corrected cure status at Day 29 can be defined.

Important protocol deviations for exclusion from the PPS will be identified by the clinical team before database lock.

The PK set is a subset of the Full Analysis Set who had evaluable PK parameter data.

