In order to support an early readout of the study based on observed PK, efficacy and safety, enrollment may be stopped. Thereafter, the criterion of 0.337 for the observed half width of 2-sided 90% CI for the log concentration will be increased to a threshold that is appropriate for the sample size.

Additional modeling and simulation may be performed to support the planned analyses.

4 Change to protocol specified analyses

No change from protocol specified analysis was made.

5 Appendix

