5.8 Rule of exclusion criteria of analysis sets

Table 5-7 Protocol deviations and non-PD criteria leading to exclusion from analysis sets ce values for PK analyses

Analysis Set	PD (description and ID) that causes subjects to be excluded	Non-PD criteria that cause subjects to be excluded
FAS	Informed Consent for study participation not obtained (INCL05) Plasmodium falciparum not present as parasite species at Screening visit (INCL04)	No study drug taken
SAF	Informed Consent for study participation not obtained (INCL05)	No study drug taken
PPS	Baseline Plasmodium falciparum parasite count is not ≥ 500 and $< 100,000/\mu\text{L}$ at screening visit for patients in Cohort 1 (INCL04A) Baseline Plasmodium falciparum parasite count is not ≥ 100 and $< 100,000/\mu\text{L}$ at	Not in FAS Did take less than 80% of planned study medication (see Section 2.4.1) PCR corrected cure status at Day 29 can not be defined Not classified as non-responder before Day 8, no positive blood smear parasite on Day 8

Analysis Set	PD (description and ID) that causes subjects to be excluded	Non-PD criteria that cause subjects to be excluded
	screening visit for patients in Cohort 2 (INCL04B)	onwards, and blood smear parasite result is missing at Day 29.
	Prohibited concomitant anti-malarial medication administered without experiencing ETF, LCF, LPF (PROH02)	Not classified as non-responder before Day 8, have at least one positive blood smear parasite result between Day 8 and Day 29 which cannot be determined as recrudescent or new infection based on PCR genotyping.
	Prohibited concomitant non-malaria medications with potential impact on efficacy/antimalarial activity (PROH01A)	
	Presence of another critical condition (EXCL06)	
PK		Not in FAS
		No evaluable PK parameter data available

6 References

Stepniewska K, White NJ (2006) Some considerations in the design and interpretation of antimalarial drug trials in uncomplicated falciparum malaria. *Malar J*; 5: 127.

World Health Organization (2015) Guidelines for the treatment of malaria. Third Edition.

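### SAP 2.2 and 5.8 narrow the protocol's Full Analysis Set without declaring it, so a dosed infant without P. falciparum at Screening drops out of the primary artemether Cmax analysis

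*SAP*

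**What the plan says.** **Full Analysis Set and PK set**

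- Protocol 12.1: "The Full Analysis Set (FAS) comprises all subjects that received any study drug". The PK set is the part of the FAS with evaluable PK parameter data.
- SAP 2.2: the FAS "comprises all subjects that received any study drug and had *Plasmodium falciparum* present at Screening visit". The PK set is again a subset of the FAS.
- SAP 5.8, FAS row, lists as a reason for removal "Plasmodium falciparum not present as parasite species at Screening visit (INCL04". The PK row removes anyone not in the FAS. The Safety Set row does not carry the parasite condition.
- SAP 2.5 and 2.6 run the primary artemether Cmax and the key secondary Day 8 lumefantrine concentration on the PK set.
- SAP 4: "No change from protocol specified analysis was made".

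**Per-Protocol Set**

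- Protocol 12.1 and SAP 2.2 give the same criteria, including freedom from important deviations affecting efficacy. The clinical team identifies these before database lock.
- SAP 5.8 lists five deviation codes for the PPS: INCL04A and INCL04B (parasite density out of range), PROH01A, EXCL06, and PROH02, worded "Prohibited concomitant anti-malarial medication administered without experiencing ETF, LCF, LPF (PROH02".
- Protocol 5.2 excludes, as no. 15, "Patients who received any antimalarial drug, including antibiotics with antimalarial activity, within 14 days of trial start" and, as no. 3, "Presence of severe malaria (according to WHO 2015 definition". Neither appears in any row of SAP 5.8.
- Protocol 6.2.1 defines concomitant medication as medication other than study drug "given at least once between the day of first dose of study medication and the last visit" of core follow-up.

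**The concern.** The primary endpoint is an exposure measure, chosen because artemether exposure is the main safety worry in this population (protocol 8.5.2). An infant who was dosed and sampled contributes a valid concentration whether or not the Screening slide shows P. falciparum. The SAP would report that infant's adverse events and discard the exposure that goes with them. The SAP departs from the protocol here on the primary analysis population while stating that it does not depart at all.

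The PPS carries PCR-corrected ACPR. An antimalarial taken shortly before entry, or severe malaria at entry, bears directly on efficacy, yet the table that turns the general PPS criterion into codes is silent on both. In an open-label study, what the table omits is left to judgement by people who can see the outcomes. The PK row lists no eligibility deviation either, so earlier lumefantrine could add to the Day 8 concentration.

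**Working it through.** **1. Set membership.** Take an infant who was dosed, has evaluable 1 h, 2 h and 168 h samples, and had no P. falciparum at Screening.

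| Set or analysis | Protocol 12.1 | SAP 2.2 and 5.8 |
|---|---|---|
| Safety Set | in | in |
| FAS | in | out |
| PK set | in | out |
| Primary artemether Cmax | in | out |
| Day 8 lumefantrine | in | out |

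No other Cmax analysis in the SAP brings the infant back. The sensitivity analysis in SAP 2.5.4 uses the PPS, also nested in the FAS, and the pooled supportive analysis uses the PK set. The case should be rare, since protocol 8.3 bars patients with a negative slide. It can still arise: slides are read locally and again centrally, Cohort 2 admits densities from 100 per µL, and the SAP does not say which reading decides INCL04.

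**2. The plan's precision figure.** Inputs from protocol 12.8.1 and SAP 3.1.1: SD of log Cmax 0.65, two-sided 90% CI, half width at most 0.337, 80% probability, n = 16.

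Half width = t(0.95; n−1) × s/√n, with (n−1)s²/0.65² chi-square on n−1 df.

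- At n = 16 the largest admissible s is 0.337 × 4/1.753 = 0.769. Then 15 × (0.769/0.65)² ≈ 21.0, and P(chi-square on 15 df ≤ 21.0) = 86.3%. Conditional on the CI covering the true mean, it is 85.2%.
- The smallest n reaching 80% is 15 unconditionally and 16 conditionally. The stated 16 is reproduced, with 80% as a floor.
- Enrolment: 16/0.90 = 17.8, so 18; 16/0.75 = 21.3, so 22. Both are as stated.

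**3. Cost of losing one infant from the PK set** (probabilities conditional on coverage).

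- From 16 to 15 evaluable: 85.2% falls to 78.7%. With s = 0.65 the half width goes from 0.285 to 0.296.
- If all 22 are enrolled and 10% are not evaluable for Cmax, about 22 × 0.90 = 19.8, or 20, remain. From 20 to 19: 98.1% falls to 96.5%.
- Effect on the estimate, assuming the dropped infant lies two SDs (1.30 on the log scale) above the mean of the other 15: keeping it moves the log mean by 1.30/16 = 0.081, or 8.5% on the geometric mean.

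**4. Reach of the PPS codes.** On the protocol 6.2.1 definition, a course completed before the day of first dose is not concomitant. The PROH02 qualifier about ETF, LCF and LPF also points to events after dosing. Severe malaria is partly caught: EXCL06 corresponds to exclusion 6 (hypotension, deteriorated condition by IMCI criteria), and INCL04A/B remove counts of 100,000 per µL or more. Cases resting only on findings such as hypoglycaemia or acidosis are not caught by a listed code.

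**5. Size of the PPS and carry-over effects, on assumed counts.**

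- One infant among 16 carries 1/16 = 6.25 points of a cure rate. If two cured infants are removed, 14/16 = 87.5% becomes 12/14 = 85.7%, a shift of 1.8 points. The 95% Clopper-Pearson interval for 14/16 is about 62% to 98%.
- Lumefantrine half-life is about 5 days (protocol 1.1). Take 212 to 666 ng/mL (the Day 8 geometric means in SAP Table 5-6) as an assumed level at study entry. After 7 days the factor is 2^(−7/5) = 0.379, leaving 80 to 252 ng/mL. Added to one of 16 infants at the modelled 270 ng/mL (protocol Table 4-2), this multiplies the geometric mean by (350/270)^(1/16) = 1.016 to (522/270)^(1/16) = 1.042.

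**The case against.** **On the FAS and PK set.** The target population is infants with malaria, and infection may affect absorption, so one could argue that an uninfected infant does not belong in the PK analysis. That would support a declared change; it does not support an undeclared one. Protocol Table 2-1 also states the PK objectives for infants and neonates under 5 kg dosed with the formulation, and reserves the malaria condition for the safety and efficacy objectives. The point that such infants should be few stands.

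**On the PPS.** The case against is stronger here, and most of it stands.

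- A reader might infer that pre-treated or severely ill infants remain in the PPS. The documents do not support that. The general criterion lets the clinical team remove them before lock, and SAP 5.8 does not claim to be exhaustive.
- A reader might infer that the PPS list contradicts the protocol. It does not: the criteria in SAP 2.2 match protocol 12.1.
- PROH02 can be read more widely. Protocol 12.3 and SAP 2.4.2 speak of concomitant medication before as well as after the start of treatment, and Table 6-2 prohibits antimalarials before entry. The wording is ambiguous; it does not prove an omission.
- A pre-treated infant would not simply be an earlier drug's cure credited to study drug. INCL04A/B require at least 500 (Cohort 1) or 100 (Cohort 2) parasites per µL at Screening for the PPS, so the earlier drug had not cleared the infection.

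**On the neonatal PK check.** It is tempting to say that one dropped infant would be one of three at the first Cohort 2 check. Protocol 12.7 calls these checks informal, SAP 2.1 runs them on raw-data reports, and the amendment rationale says Cohort 2.1 had completed enrolment. Nothing shows that SAP 5.8 governs them.

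**Conclusion.** The main point holds. SAP 2.2 and 5.8 conflict with protocol 12.1 on who is in the FAS, the PK set inherits the conflict, and SAP 4 is wrong to declare no change. The consequence is loss of a valid primary Cmax and Day 8 lumefantrine value for any dosed infant without P. falciparum at Screening. One such infant costs 6.5 percentage points of precision probability at 16 evaluable (85.2% to 78.7%) and under 2 points at 20. This assumes the plan's SD of 0.65. The number of such infants is not given and may be zero.

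The secondary point holds only as an omission from a list. Exclusions 3 and 15 are attached to no set in SAP 5.8, and PROH02 does not clearly cover a course finished before the first dose, so the decision is left open rather than made wrongly. The effect per infant is small: at most 6.25 points of a 16-patient cure rate, and about 1.6% to 4.2% on the Day 8 geometric mean against a planned CI factor of 1.4. Carry-over would, however, push towards success, because SAP 2.6.2 asks only that the upper confidence limit not fall below the historical value. These sizes rest on assumed counts and an assumed residual level.

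**What to change.** Before database lock:

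1. In SAP 2.2 and 5.8, define the PK set as all treated infants with evaluable PK parameter data. Apply the P. falciparum condition only to the efficacy analyses, and state whether the local or central slide reading decides it.
2. Record in SAP 4 whatever departure from the protocol FAS remains, including its use for efficacy. If the narrower PK set is kept, declare that too and add a sensitivity analysis of artemether Cmax and Day 8 lumefantrine on all treated infants.
3. Add violations of exclusions 3 and 15 to the PPS row, or state why they do not affect efficacy. Say whether PROH02 covers antimalarials taken before the first dose.
4. Report Day 8 lumefantrine with infants known to have had recent prior lumefantrine excluded from that analysis only. Define recent explicitly: exclusion 15 uses 14 days while protocol Table 6-2 uses five half-lives for antimalarials, and the two need reconciling.

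The cost is a few lines in SAP 2.2, 4 and 5.8, plus a short extra table. No EXCL03 or EXCL15 code appears in SAP 5.8, so the sponsor should check that these deviations are captured. The downside is possibly one or two fewer PPS patients.

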6.2.3 Rescue medication

The following circumstances warrant discontinuation of study treatment (during the treatment period) and the implementation of rescue medication by the investigator (Commencement of rescue medication may occur after the start of study drug and up to Day 43):

Early Treatment Failure (ETF)

- Development of danger signs or severe malaria on Day 2, Day 3, Day 4 in the presence of parasitemia.
- Parasitemia on Day 3 higher than Day 1 count irrespective of axillary temperature.
- Parasitemia on Day 4 with axillary temperature $\geq 37.5^\circ$.
- Parasitemia on Day 4 equals to or more than 25% of count on Day 1.

Late Clinical Failure (LCF)

- Development of danger signs or severe malaria on any day from Day 5 to Day 43 in the presence of parasitemia without previously meeting any of the criteria of Early Treatment Failure.
- Presence of parasitemia and axillary temperature $\geq 37.5^\circ$ on any day from Day 5 to Day 43 without previously meeting any of the criteria of Early Treatment Failure.

Late Parasitological Failure (LPF)

- Presence of parasitemia on any day from Day 8 to Day 43 and axillary temperature $< 37.5^\circ$ without previously meeting any of the criteria of Early Treatment Failure or Late Clinical Failure.

Rescue treatment involves therapy with an effective antimalarial available locally as per local medical practice or National Treatment Guidelines. Administration may be oral or parenteral depending on the subject's clinical condition. Rescue treatment will not be considered study medication. The exact rescue regimen and route of administration must be recorded on the appropriate CRF.

Patients will be monitored, either in clinic, or via home visits for the duration of treatment to ensure adherence to the rescue medication therapy. These patients will not discontinue the study (i.e., all the examinations as per the assessment schedule and all CRF for this patient will need to be completed), and they will not be replaced (unless the PK data cannot be properly analyzed due to treatment schedule discontinuation).

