In addition, central reading of all slides will be performed at a central reference laboratory. The results of the local reading will be entered in the (e)CRF and results of the central readings will be sent electronically by the central laboratory to Novartis (or a designated CRO). Results from the central reading will be used for the derivation of primary and secondary efficacy endpoints.

Blood samples for molecular diagnostic purposes

Blood will be sampled for parasite genotyping (PCR) as indicated in the assessment schedule ([Table 8-1](#)). At screening, a blood sample will be collected in all patients fulfilling eligibility criteria for inclusion in the study. A second blood sample will be analyzed only in patients showing treatment failure. This will allow to distinguish between recrudescence and a new infection. Sample analysis will be performed at a pre-selected reference laboratory.

Microscopic species identification (parasitemia) will be confirmed and determined with PCR-based methods on blood retained from samples collected at the time of treatment failure.

All parasite samples at baseline will also be screened for specific genes/single-nucleotide polymorphisms (SNPs) that are known as markers for *P. falciparum* resistance.

During the analysis process no human DNA will be amplified or analyzed by any means.

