2.7.2.1 PCR-corrected ACPR and uncorrected ACPR

At each visit, the ACPR rate with 95% 2-sided confidence intervals will be provided using the Clopper-Pearson method for each treatment group by cohort using PPS for PCR-corrected ACPR and FAS for uncorrected ACPR.

Data will be handled as follows:

- Treatment failures after 7 days (i.e., Study Day 8) due to new infections based on PCR genotyping are not considered as failure for PCR-corrected analyses.

- For uncorrected ACPR, patients will be treated as failure on and after the visit when a reinfection with *P. falciparum* or other species is detected (which might be either recrudescence or a new infection).
- Patients who received rescue medication for the treatment of *P. falciparum* malaria (except for the treatment of a new infection) will be considered treatment failures. Patients who received other concomitant medication having an effect on malaria for reasons other than rescue therapy e.g., for the treatment of *P. vivax* (e.g., primaquine, certain antibiotics (sulfonamides, tetracycline, etc.) will be considered in the analysis as if they had not taken the drug.
- Patients will be counted as failure at a visit (e.g. Study Day 15, etc.) if (a) they did not have a parasite count, i.e., missing parasite count at that visit unless these patients could be classified as cured based on absence of parasitaemia (parasite count = 0) at a later time (e.g., Study Day 29), or (b) they did not have valid PCR evaluations at baseline and the visit if parasitaemia was present at that time (e.g., Study Day 15).
- For intermediate missing data, (a) once a patient experienced a treatment failure at a timepoint (eg. Day 15), the patient is considered as treatment failure at all later timepoints (eg. Day 29), (b) if a patient is considered as cured at a timepoint (eg. Day 29), the patient is considered as cured at earlier timepoints (eg. Day 15).

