2.7.2.2 Recrudescence and new infection

New infection is defined as appearance of asexual parasites after clearance of initial infection with a genotype different from those parasites present at baseline. New infection must be confirmed by PCR analysis.

Recrudescence is defined as appearance of asexual parasites after clearance of initial infection with a genotype identical to that of parasites present at baseline. Recrudescence must be confirmed by PCR analysis.

Incidence rates of recrudescence and new infection at Days 15, 29 and 43 will be estimated by Kaplan-Meier method based on the subset of FAS patients who have clearance of initial infection by Day 7. Time to event (recrudescence or new infection) will be calculated from the time of first study medication to the date of first event if a patient experiences the event and be censored at the time of last parasite assessment if a patient does not experience the event.

Patients with new infection will be censored at the time of first new infection when analyzing time to recrudescence. Patients with recrudescence will be censored at the time of first recrudescence when analyzing time to new infection. Undetermined treatment failures due to missing PCR data will be considered as censored at the time of treatment failure.

Time (event or censored) will be truncated at Day 43 to avoid sudden drop in number of patients at risk after Day 43.

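### As worded, the last PPS exclusion in SAP 5.8 can drop an infant with a PCR-proven recrudescence who also has another, untyped positive film

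*SAP*

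**What the plan says.** SAP 2.2 and Protocol 12.1 define the PPS by three conditions. The relevant one is that "PCR corrected cure status at Day 29 can be defined".

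SAP 2.7.2.1 computes PCR-corrected ACPR in the PPS, with Clopper-Pearson 95% intervals. Its data rules include:

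- Carry-forward of failure: "once a patient experienced a treatment failure at a timepoint (eg. Day 15), the patient is considered as treatment failure at all later timepoints".
- Missing PCR: a visit with parasitaemia but without valid PCR at baseline and at that visit counts as a failure at that visit.
- New infections shown by genotyping after 7 days are not failures in the PCR-corrected analysis.

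SAP 5.8, Table 5-7, turns the PPS definition into exclusion criteria. The non-deviation column lists undefined Day 29 status, followed by two clauses about films. The second clause excludes infants who "have at least one positive blood smear parasite result between Day 8 and Day 29 which cannot be determined as recrudescent or new infection" by PCR genotyping. Its only guard is the opening condition, "Not classified as non-responder before Day 8".

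On sampling, Protocol 8.3 says: "A second blood sample will be analyzed only in patients showing treatment failure". Table 8-1 shows conditional PCR samples at Days 8, 15, 29 and 43. Of rescued infants, Protocol 6.2.3 says: "These patients will not discontinue the study". Protocol 8.3 has every slide re-read centrally and states: "Results from the central reading will be used for the derivation of primary and secondary efficacy endpoints".

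**The concern.** The definition in SAP 2.2 asks whether the Day 29 status is known. The film clause in Table 5-7 asks something else: whether any positive film from Day 8 to Day 29 lacks a type. The two questions give different answers for an infant who has one film typed as recrudescence and another that PCR cannot type. The status is known to be failure, yet the clause read literally removes the infant. The guard does not help, because it covers only failure before Day 8.

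Removing an established failure from the denominator while the number cured stays the same can only raise the Day 29 and Day 43 rates. The same holds at Day 15 if the failure is established by then. With about 22 infants per cohort, one infant is visible in the estimate. The sensitivity analysis in SAP 2.7.2.1.2 starts from the same PPS and would inherit the omission. SAP section 4 reports no change from the protocol's analyses, so a narrower PPS would also be undeclared.

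**Working it through.** **Step 1. Apply the rules to one infant.** Suppose the infant is not a failure before Day 8, has a PCR-confirmed recrudescence at Day 15, and has a second positive film at Day 8 or Day 29 without a usable PCR result.

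| Rule | Result |
|---|---|
| SAP 2.7.2.1, carry-forward | Failure at Day 15, therefore failure at Day 29 |
| SAP 2.2 and Protocol 12.1 | Day 29 status is defined, so the infant stays in the PPS |
| SAP 5.8, guard | Not a non-responder before Day 8, so the guard does not spare the infant |
| SAP 5.8, film clause | At least one untyped positive film, so the infant is excluded |

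The last row contradicts the second. With the recrudescence alone and no second untyped film, the clause is not triggered and there is no conflict.

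**Step 2. Can the second film arise?** Rescued infants keep attending visits with films, a central reading can turn a locally negative film positive, and genotyping can fail. Against this, Table 8-1 plans a conditional PCR sample at each scheduled visit from Day 8 to Day 29. The combination is possible, but the documents give no rate for it.

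**Step 3. Denominator.** The plan gives no expected ACPR and no figure for this clause. Its enrolment figure is reproduced: 16 / (1 − 0.25) = 21.3, rounded up to 22 per cohort. I use 16 to 22 as the range for the PPS.

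**Step 4. Effect of dropping one failure.** With n infants and f failures, the rate moves from (n − f)/n to (n − f)/(n − 1), a shift of (n − f)/[n(n − 1)]. Exact limits are the Beta quantiles B(0.025; x, n − x + 1) and B(0.975; x + 1, n − x). The failure counts are assumptions.

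| n | f (assumed) | Failure kept (95% CI) | One failure dropped (95% CI) | Shift, points |
|---|---|---|---|---|
| 22 | 1 | 21/22 = 95.5% (77.2–99.9) | 21/21 = 100% (83.9–100) | 21/462 = 4.5 |
| 22 | 2 | 20/22 = 90.9% (70.8–98.9) | 20/21 = 95.2% (76.2–99.9) | 20/462 = 4.3 |
| 22 | 3 | 19/22 = 86.4% (65.1–97.1) | 19/21 = 90.5% (69.6–98.8) | 19/462 = 4.1 |
| 20 | 2 | 18/20 = 90.0% (68.3–98.8) | 18/19 = 94.7% (74.0–99.9) | 18/380 = 4.7 |
| 16 | 1 | 15/16 = 93.8% (69.8–99.8) | 15/15 = 100% (78.2–100) | 15/240 = 6.3 |
| 16 | 2 | 14/16 = 87.5% (61.7–98.4) | 14/15 = 93.3% (68.1–99.8) | 14/240 = 5.8 |

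If no infant has both a typed recrudescence and an untyped film, the shift is zero.

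**Step 5. A related conflict.** An infant whose only positive film is untyped is a failure under the missing-PCR rule in SAP 2.7.2.1. Table 5-7 removes that infant from the set in which the rule is applied. For positive films from Day 8 to Day 29, the two sections cannot both operate as written.

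**The case against.** The strongest reply is that the film clauses follow directly on the criterion of undefined Day 29 status and may only illustrate it. On that reading a proven recrudescence has a defined status and stays in. This may well be the intent, and the layout of the table cannot be judged from the extracted text. But the clause does not say so, and a program coded from its words would exclude the infant.

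The reply on impact also stands in part. ACPR is a secondary endpoint without a hypothesis. The FAS analyses (Kaplan-Meier PCR-corrected ACPR, uncorrected ACPR and recrudescence incidence) do not use the PPS exclusions, so a dropped failure could be seen elsewhere in the report. They do not correct the PPS rate itself.

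Four stronger readings are tempting, and the documents do not support them:

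- **That every infant with a proven recrudescence is removed.** A second, untyped positive film in the window is needed.
- **That extra untyped films are to be expected.** The sentence about a second sample, read alone, suggests this. The conditional samples in Table 8-1 make such films possible, no more.
- **That the clause removes only failures.** An infant with a typed new infection and an untyped film is caught too, and the typed new infection is not a PCR-corrected failure.
- **That an infant who never clears must be excluded as untypable.** SAP 2.7.2.2 says: "Recrudescence is defined as appearance of asexual parasites after clearance of initial infection". But the Table 5-7 clause tests PCR genotyping, and a genotype identical to baseline can be read as not a new infection.

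**Conclusion.** The point holds as a defect of wording. Taken literally, the last PPS clause in Table 5-7 excludes an infant whom SAP 2.2 and SAP 2.7.2.1 together classify as a failure belonging in the PPS. The bias is upward whenever such an infant is dropped: about 4 to 6 points on Day 29 PCR-corrected ACPR per infant, at 16 to 22 infants and with 1 to 3 assumed failures. That is small beside intervals some 20 to 37 points wide, but it goes in one direction and is avoidable. The number of infants affected cannot be derived from the documents and may be zero, so it should not be inferred that the reported cure rate will be inflated.

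**What to change.** In SAP 5.8, add to the film clause: and no treatment failure (including PCR-confirmed recrudescence) otherwise established by Day 29. Say that treatment failure here means failure in the PCR-corrected sense. A positive film from Day 8 onward can meet the late-failure definitions in SAP 2.1.1.1 whatever its genotype, so an unqualified exception could swallow the clause.

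State that an infant with an established failure stays in the PPS as a failure whatever other films show. Do not write the limit as a test of the first positive film only. A typed new infection followed by an untyped film would then stay in the PPS with its Day 29 status unresolved.

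Reconcile the clause with the missing-PCR rule in SAP 2.7.2.1, by saying whether an infant whose only positive film is untyped is excluded or counted as a failure, and use the same rule in both places.

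The cost is a few sentences in the SAP and a small change to the PPS program, before database lock. No new data are needed. The reported cure rate may be slightly less favourable.
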